10.4 Safety analysis

Adverse events will be summarised in frequency tables by study product, containing number of subjects with no AEs, number of subjects with at least one AE, and number of events, subdivided by related/unrelated, serious/non-serious. All AEs will be summarised and listed by system organ class (SOC) and preferred term (PT) assigned using MedDRA. Furthermore, AEs will be summarised by causality, and both related and unrelated events will be summarised separately by maximum intensity. For related AEs, i.e. AEs judged by the Investigator or Sponsor to be related to the study product and/or study product injection procedure, the number of days to onset and the duration of the event will be summarised by PT.

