ICH	International Conference on Harmonisation
IEC	Independent ethics committee
IFU	Instructions for use
IUD	Intra uterine device
Institution	Any public or private entity or agency or medical or dental facility where a clinical study is conducted.
Investigator	The Principal Investigator (PI) or other qualified person, i.e. sub-Investigator, designated and supervised by the PI at a study site to perform critical study-related procedures or to make important study-related decisions as specified on the signature and delegation log
Investigator file	Essential documents relating to a clinical study as defined in applicable GCP guidance document and maintained by the Investigator.

	Title	Doc id
👶 GALDERMA	05DF1910 Clinical Study Protocol	
		MA-42248

Abbreviation/Term	Definition
IPL	Intense Pulsed Light
IPR	Independent Photographic Reviewer
ISO	International Organization for Standardization
MDR	Medical Devices Regulation
MITT	Modified intention-to-treat
ML	Marionette lines
MedDRA	Medical dictionary for regulatory activities
NLF	Nasolabial fold
NSAID	Non-steroidal anti-inflammatory drug
OBT	Optimal Balance Technology
PI	Principal Investigator; qualified person responsible for conducting the study at a study site
PT	Preferred term
SAE	Serious adverse event
SDV	Source data verification
SOC	System organ class
Sponsor file	Essential documents relating to a clinical study as defined in applicable GCP guidance document and maintained by the Sponsor.
Study files	The Investigator file and the Sponsor file
Study products	The investigational product and the reference product under study
Study site	Institution or site where the study is carried out
Touch-up	Repeated injection to be performed after treatment, if necessary to achieve optimal correction
U-HCG	Urinary human chorionic gonadotropin
UTW	Ultra-Thin Wall
WHO	World Health Organization

Lucie				
05DF1910	Clinical	Study	Proto	col

Doc id

MA-42248

Tab	le of	Cont	tents
-----	-------	------	-------

INVE	NVESTIGATORS AND STUDY ADMINISTRATIVE STRUCTURE	
SYNO	SYNOPSIS	
ABBR	REVIATIONS AND DEFINITIONS OF TERMS	10
LIST	OF TABLES	15
LIST	OF FIGURES	15
LIST	OF APPENDICES	15
1. H	ETHICAL CONSIDERATIONS	16
1.1	Statement of ethical compliance	16
1.2	Application to independent ethics committee	16
2. H	BACKGROUND INFORMATION	17
2.1	Indication and population description	17
2.2	Study Product Profile	17
2.2.1	Investigational product description	17
2.3	Study rationale and justification for design	18
2.4	Risks and benefits	18

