2.2.1.2 Clinical documentation

The first injectable OBT gel product was CE-marked in Europe in 2009. Several studies have been conducted to assess the safety and efficacy of OBT products in the treatment of e.g. cheeks, NLFs, and lips 6-10.

Study rationale and justification for design 2.3

This study aims to document the results of a stepwise treatment and determine if any of the two approaches to be used in this study, down-up and top-down, affects the studied endpoints. Results from the study will be the basis for future treatment guidelines used by aesthetic health care practitioners when injecting Restylane Defyne in the chin, NLF and ML.

Approximately 60 subjects (of which at least 20 males) will be enrolled and randomized into two groups with different treatment schedules. Comparison between the two groups will help to determine if the different treatment approaches affects the outcome, such as subject satisfaction.

Risks and benefits

After the injection of the study products, some common injection-related reactions might occur. These reactions include erythema, swelling, pain, itching, bruising or tenderness at the implant site. Typically, resolution is spontaneous within a few days after injection.

There is a risk that the subject will not gain the full aesthetic correction of the treated areas. There is also a risk for development of palpable HA lumps or displacement of the injected HA. Inflammation or infection has been reported in a few cases after treatment. There may be risk of bruising and/or damaging body structures such as nerves or blood vessels connected to the injection site, however these risks are minor.

Following facial aesthetic treatments isolated rare cases have been reported regarding ischemic events affecting the eye leading to visual loss, and the brain resulting in cerebral infarction. Detailed information on reported adverse events (AE) relevant for the study product is provided in the instructions for use (IFU).

Lidocaine can in rare cases give allergic reactions, and therefore subjects with known allergy or hypersensitivity to local anaesthetics should not be included in the study.

Given the anticipated low level of transient and acceptable AEs in connection with the injection, the risk-benefit assessment of the use of the study products for lower face augmentation offers a potential clinical benefit, such as subject rated improvement of attractiveness and satisfaction, at reasonable risk.

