3.1.2 Safety objective and endpoints

Objective:

To evaluate AEs collected throughout the study

Endpoint

Incidence, intensity, duration and onset of AEs collected from injection of study product to patient withdrawal or end of study (visit 5).

Design of the Study

General outline

This is a 12-week, randomized, male-female and site stratified, evaluator-blinded, multicentre study to evaluate the effectiveness and safety of Restylane Defyne when using two different injection approaches, stepwise down-up vs. top-down, when treating the lower face.

Approximately 60 subjects requiring augmentation and correction therapy in the chin, NLFs and MLs fulfilling all eligibility criteria will be enrolled in the study. The subjects will be randomized to one of two treatment groups, the first treatment group will receive injections in the chin area at baseline and in the NLFs and MLs at the visit 3 (week 3), the second group will undergo the same treatment but in reverse order. The two groups are referred to as downup and top-down. Male-female stratification will be applied in the randomization and the aim is to randomize 10 male subjects to each group.

[figure not shown]
Doe id 05DF1910 Clinical Study Protocol 🚣 GALDERMA MA-42248

Six weeks after the second treatment, at visit 4, an optional touch-up will be administered to subjects that have not obtained optimal aesthetic improvement as agreed between subject and Investigator.

The subject will return to the clinic for a final follow-up visit (visit 5) 9 weeks after the first treatment.

All efficacy study assessments will be performed before treatment and safety will be followed by AE and device deficiency reporting throughout the study.

The Investigator will assess, Global Aesthetic Improvement Scale (GAIS), naturalness/ and safety. The subject assessments include, subject satisfaction questionnaire.

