- Safety reasons: If a subject suffers an AE, which in the judgment of the Investigator or the Sponsor presents an unacceptable consequence or risk to the subject.
- Withdrawal of informed consent: A subject can withdraw their consent to participate
 in the study at their own request or be withdrawn from participation in the study at the
 request of their legally authorised representative at any time for any reason.
- Lost to follow-up: If a subject does not return for a scheduled visit, reasonable effort shall be made to contact that subject, e.g. call three times at different hours and leave messages if applicable before declaring the subject lost to follow-up.
- Other: Examples of other reasons for withdrawal may be failure to comply with protocol requirements or to complete the protocol-specified evaluations.

If reason for discontinuation is "withdrawal by subject" or "other", the subject will be questioned to rule out the possibility of an AE. If the AE led to discontinuation then "adverse event" should be chosen as the reason for discontinuation, rather than "withdrawal by subject" or "other".

If an AE which, according to the Investigator's assessment, is related to the use of any of the study products and is still ongoing at the time of the withdrawal, the Investigator shall follow-up the subject until the AE resolves, is assessed by the Investigator to be "chronic" or "stable" or for at least 3 months.

Subjects who have received prohibited concomitant medications or therapies should be followed according to protocol.

6. Study Products

The term "study product" refers to Restylane Defyne.

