10.2 Demographics, baseline assessments, and subject characteristics

Demographic endpoints and subject characteristics will be presented by investigational product using descriptive statistics.

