10.3 Efficacy analysis

All analyses will be performed by treatment group and in total.

The GAIS assessment will be presented in frequency tables at each follow-up visit and for each evaluator separately (/Investigator). In addition, the proportion of improved subjects (assessed as very much improved, much improved or improved) will be presented together

The subject satisfaction questionnaire assessments will be presented in frequency tables at each applicable visit. For the questions where the answer is given using an agreement scale the number and percentage of subjects agreeing (Definitely agree/Somewhat agree) to the assessment will also be presented.

The evaluation of naturalness, will be presented in frequency tables at each follow-up visit and for each evaluator separately /Investigator).

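### Sections 10.2 and 10.4 tabulate baseline data and adverse events by product, but both arms receive the same product, so the tables as written do not separate the two randomised groups.

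*Combined protocol and SAP*

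**What the plan says.** Section 10 uses three different grouping labels.

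- 10.2, baseline: "Demographic endpoints and subject characteristics will be presented by investigational product using descriptive statistics".
- 10.3, efficacy: "All analyses will be performed by treatment group and in total".
- 10.4, safety: "Adverse events will be summarised in frequency tables by study product". This sentence covers the overall table of subjects with and without AEs and the number of events. The later summaries in 10.4 (SOC and preferred term, causality, maximum intensity, onset, duration) name no treatment grouping.

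Section 6 states that the term study product "refers to Restylane Defyne". The abbreviations list defines the plural differently, as "The investigational product and the reference product under study", but no reference product is named anywhere in this trial. Under 4.1, both arms get the same treatment in opposite order.

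**The concern.** A grouping variable with one level produces one column. A baseline table and an overall AE table split by product would therefore pool the two arms. The labels look carried over from a template for a trial that compares two products.

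Three things are at stake.

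- **The study aim.** Section 2.3 says the study is to "determine if any of the two approaches to be used in this study, down-up and top-down, affects the studied endpoints". Section 3.1.2 gives the safety endpoints as "Incidence, intensity, duration and onset of AEs collected from injection of study product", up to withdrawal or end of study. Section 4.1 describes a study "to evaluate the effectiveness and safety of Restylane Defyne when using two different injection approaches", and 10.8 justifies the sample size by reference to the effectiveness and safety of both approaches. A pooled AE table does not address a comparison of approaches.
- **Baseline comparability.** Under 4.4.1, randomisation is stratified by site and gender only. With about 30 per arm, age, skin type or previous facial treatments can be unbalanced by chance. The 10.2 table is where a reader would see this.
- **Subjects outside the efficacy set.** Under 10.1, the MITT population requires treatment at both baseline and week 3, and all efficacy analyses use it. A subject who stops after the first session is left only in the safety population. Pooled safety summaries would not show which approach that subject received.

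**Working it through.** The plan gives no figure to reproduce here. The check is a count of levels, followed by arithmetic on what pooling can hide.

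**1. Levels of each grouping variable**

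| Table | Grouping named | Levels | Columns |
|---|---|---|---|
| Baseline (10.2) | investigational product | 1 | one, about 60 |
| Overall AE table (10.4) | study product | 1 | one, about 60 |
| Other AE summaries (10.4) | none | – | not specified |
| Efficacy (10.3) | treatment group and total | 2 + total | about 30, about 30, about 60 |

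The wider definition in the abbreviations list does not supply a second level, because there is no reference product. So 10.2 and the first sentence of 10.4 specify pooled tables, while the rest of 10.4 is unclear rather than pooled.

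**2. Whether the arms differ in a way that bears on AEs**

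Section 6.5.2 allows up to 4 mL in total for the chin session, and up to 2 mL per NLF and 2 mL per ML for the other session. Assuming two of each line, the second figure is 2 × 2 + 2 × 2 = 8 mL, and 4 + 8 = 12 mL agrees with the stated total for visits 2 and 3. The permitted first-session volume is therefore 4 mL in down-up and 8 mL in top-down, so AE incidence and onset by arm is a real question.

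**3. What a pooled count can hide**

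The documents give no AE rate, so a range is shown, assuming 30 per group. For a pooled count x out of 60 (x even, x ≤ 30), the smallest between-group difference is 0 (x/2 in each arm) and the largest is x/30 (all in one arm).

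- x = 6 (10%): 0 to 6/30 = 20 points.
- x = 18 (30%): 0 to 18/30 = 60 points.
- x = 30 (50%): 0 to 30/30 = 100 points.

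These are arithmetic limits, not expected differences.

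**4. What by-group tables would add**

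With equal true rates p and 30 per group, the 95% CI half-width for the difference is 1.96 × √(2p(1 − p)/30).

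- p = 0.10: 1.96 × √0.00600 = 0.152, about 15 points.
- p = 0.30: 1.96 × √0.01400 = 0.232, about 23 points.
- p = 0.50: 1.96 × √0.01667 = 0.253, about 25 points.

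By-group AE tables would describe the arms and reveal large differences. They would not establish or exclude moderate ones.

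**The case against.** The strongest reply is that pooling AEs may be deliberate. The safety objective in 3.1.2 is simply to evaluate AEs collected during the study. Both arms receive the same on-label product in the same areas, and the example outcome in 2.3 is subject satisfaction, which is already reported by arm. This stands in part: pooled AE tables would satisfy the 3.1.2 objective. They would not serve the comparative aim in 2.3 or the statements about the safety of the two approaches in 4.1 and 10.8. Nor does the argument help the baseline table.

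A second reply is that the opening sentence of 10.3 is unqualified and any statistician would tabulate by arm anyway. That is probably what would happen. But the sentence sits under the efficacy heading, and 10.2 and 10.4 each name a different grouping, so at best the text conflicts with itself.

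A third reply is that the grouping may be stated elsewhere. The synopsis entry on statistical method is blacked out, and 10.7 mentions a statistical plan that is not in the supplied text. This limits the finding to section 10 as visible: it cannot be said that by-group tables are planned nowhere. It does not make the wording of 10.2 and 10.4 correct.

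It is also true that no estimate, error rate or allocation changes, and that the tables could be produced later because the arm is recorded.

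**Conclusion.** The point holds on the visible text. Sections 10.2 and 10.4 specify a baseline table and an overall AE table with one pooled column of about 60 subjects, where the design calls for two columns of about 30 plus a total. For the remaining AE summaries the plan does not say.

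The consequence is moderate. Followed literally, baseline comparability and AEs by approach would go unreported, although the approach is the only thing that was randomised. Against that, no data are lost, and by-group AE comparisons would be descriptive in any case, with half-widths of about 15 to 25 points at true rates of 10% to 50%. Those figures assume 30 per group and illustrative AE rates; the conclusion about table layout does not depend on them. The wording should be corrected.

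**What to change.** In 10.2 and in the first sentence of 10.4, replace the product label with treatment group (down-up, top-down) plus a total column. Add one sentence to 10.4 stating that this grouping applies to every AE summary in the safety population, including SOC and preferred term, causality, maximum intensity, onset and duration. If a separate statistical plan exists, check that it uses the same grouping. The definition of study products in the abbreviations list could be aligned with section 6 at the same time.

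The cost is two wording changes and one added sentence. Data collection is unchanged.

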6.5.5 Electronic case report form recordings

The treatment is a gel injected by the Investigator and the following details of the injection are to be recorded in the eCRF:

- Local anaesthetic used (product name, amount applied, application date, and concentration)
- · Date for administration
- Administered volume
- Injection technique, see list below.
- Depth of injection
- Area of injection
- Post-treatment care (e.g. moulding, ice-pack)
- Use of needle
- Size of needle

In addition, any technical problems (device deficiencies) or clinical complications associated with the injection will be recorded in the eCRF.

Injection technique to be recorded in source data and the eCRF[‡]:

- Antegrade linear threading: also called push-ahead technique as some product is pushed ahead of the needle. Once the needle is in place, the product is injected ahead while inserting the needle in the tissue.
- Retrograde linear threading: the needle is threaded into the tissue at the appropriate depth, and the product in injected as a straight line on withdrawal of the needle
- Serial puncture: numerous small needle insertions to deliver a small amount of the product, repeated along a line or regions of the tissues
- Micro-bolus: small aliquots of the product is injected along a line or regions of the
- Fanning: a number of linear threads to spread the product over a wider area
- Cross-hatching: combines multiple injections of linear threading that crisscross at right angle to provide volume in a square shape
- Other: at the choice of the treating Investigator

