8.1.3 Recording instructions

Each subject should be questioned about AEs at each study visit following signing of informed consent. The question asked should be: "Since your last clinical visit; have you had any health problems?". Information on AEs can also be obtained from signs and symptoms detected during each examination or from a laboratory test, observations made by the study site personnel, subject diaries, or spontaneous reports from the subjects or their relatives.

When an AE is related to a device deficiency (refer to section 8.2), including technical device malfunction, the AE shall be recorded on the AE form/module in the eCRF and the technical complaint shall be reported separately on the clinical study complaint form eCRF.

Investigators, or other study site personnel, shall record all AEs in the eCRF, including:

- a) Event term (recorded in standard medical terminology and avoiding abbreviations)
- b) Affected area
- c) Start date (first day with symptoms)
- d) Stop date (last day with symptoms)
- e) Intensity (mild, moderate, or severe according to definition in section 8.1.3.1)
- Seriousness (serious or not serious, according to definition in section 8.1.3.2)
- g) Causal relationship to study product or study product injection procedure (yes or no)
- h) Action taken (none, medication treatment, non-pharmacological treatment, or other procedures/tests, subject withdrawn)
- Outcome of the AE (ongoing, recovered, recovered with sequelae, death, chronic/ stable, not recovered at the end of the study)

The AE form/module in the eCRF must be signed and dated by the Investigator.

^{**} The term "life-threatening" in the definition of "serious" refers to an event in which the patient was at risk of death at the time of the event; it does not refer to an event which hypothetically might have caused death if it were more severe. (Source: ICH-E2A clinical safety data management: definitions and standards for expedited reporting).

^{††} Planned hospitalization for a pre-existing condition, or a procedure required by the CSP, without serious deterioration in health, is not considered a SAE. (Source: ISO 14155:2011).

• 6.1.55511.	Title 05DF1910 Clinical Study Protocol	Doc id
♣ GALDERMA	•	MA-42248

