10.8 Sample size

The sample size of approximately 60 subjects (30 per treatment group) is not based on a statistical calculation. The selected number of subjects is regarded as sufficient for an evaluation of effectiveness and safety of the two treatment approaches when treating the chin, NLFs and MLs with Restylane Defyne.

11. Protection of personal data

The study shall include collection and processing of personal data as specified in the Regulation (EU) 2016/679 (General Data Protection Regulation, GDPR) on the protection of

•	Title 05DF1910 Clinical Study Protocol	Doc id
♣ GALDERMA		MA-42248

individuals with regard to the processing of personal data. For the purposes of the study, Sponsor will be considered the data controller, and Institution and PI will both be considered data processors.

All processing of personal data must be carried out in accordance with national legislation concerning the protection of personal data. The Institution and the PI are responsible for complying with all requirements pursuant to national legislation in the country in which the Institution and the PI are located. The Sponsor will ensure that all requirements are complied with for data processing.

The ICF shall contain information about what personal data to be collected in the study and that this will be kept confidential. The provided information shall be sufficient to enable all subjects to give their consent not only to the participation in the study, but also to the processing of personal data. Such information includes information regarding the purposes of the collecting, processing, data transfer to countries not having same high level of security for processing of personal data than Sweden and EU, and the length of time during which personal data will be stored. The subject shall have the right of access to stored personal data, and the right to correction of incorrect information. If a subject decides to terminate the study prematurely, data collected before withdrawal of consent will be used in the evaluation of the study, however no new data may be collected. Authorized representatives from the Sponsor, contract research organization (CRO) or a CA may visit the study site to perform audits/inspections, including source data verification, i.e. comparing data in the subjects' medical records and the eCRF. Data and information shall be handled strictly confidential.

12. Quality Control and Quality Assurance

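### Section 10.4 tabulates adverse events by study product, of which there is only one, and names no reference injection for days to onset

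*Combined protocol and SAP*

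**What the plan says.** Section 10.4 opens with "Adverse events will be summarised in frequency tables by study product". It adds summaries by system organ class and preferred term, by causality and by maximum intensity. For related events, "the number of days to onset and the duration of the event will be summarised by PT". Section 6 settles how many products there are: "The term 'study product' refers to Restylane Defyne".

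The instruction "All analyses will be performed by treatment group and in total" stands in section 10.3, under efficacy, and is not repeated in 10.4.

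The safety endpoint in section 3.1.2 is worded "Incidence, intensity, duration and onset of AEs collected from injection of study product to patient withdrawal or end of study (visit 5". This fixes when AEs are collected. It does not say from which injection onset is measured.

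Section 2.3 aims to find out whether the order of treatment affects the studied endpoints. Section 10.8 says that the sample size "is not based on a statistical calculation", but regards it as sufficient to evaluate the effectiveness and safety of both approaches.

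**The concern.** The two randomised groups receive the same product in the same areas and differ only in order. A table by product therefore cannot show the one contrast that the study randomises. Followed literally, 10.4 would leave the safety half of the claim in 10.8 without a table behind it.

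Onset is a named safety endpoint, and each subject has two or three injection dates. Two programmers could follow 10.4 correctly and report different onset figures for the same data. The difference has a clinical reading: the Instructions for Use in Appendix 3 distinguish injection reactions that usually settle within a week from inflammation that can begin up to several weeks later. A first-injection clock would make an immediate reaction to the second session look delayed. A clock that always uses the latest injection could make a delayed reaction in the first-treated area look immediate.

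**Working it through.** The plan gives no onset figure to reproduce, and no power calculation bears on this point. The check is a reading of the table structure plus date arithmetic.

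**1. Columns of the AE tables.** Number of products (section 6): 1. Columns by study product: 1. Randomised groups: 2. Section 10.4 contains no statement by group, session or area.

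**2. Visit days, from Table 1, counted from visit 2**

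| Visit | Nominal day | Window |
|---|---|---|
| 3, second session | 21 | 18–24 |
| 4, optional touch-up | 42 | 39–45 |
| 5, end of study | 63 | 58–68 |

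The general outline in section 4 places visit 4 six weeks after the second treatment. That would be day 21 + 42 = 63, which is visit 5 in Table 1. The two passages must be reconciled; Table 1 is used here.

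**3. Effect of the reference date.** Onset from first injection = day of the injection preceding the event + true lag. With an assumed true lag of 1 day:

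- after the first session: 0 + 1 = 1
- after the second session: 21 + 1 = 22 (19 to 25)
- after touch-up: 42 + 1 = 43 (40 to 46)

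Onset from the latest injection is 1 in every row. The overstatement from a first-injection clock is thus 21 days (18 to 24) or 42 days (39 to 45), whatever the lag.

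**4. Effect on a mean.** Assume equal event numbers per injection given, and let u be the touch-up uptake, which the documents do not state. Mean from first injection = (1 + 22 + 43u) / (2 + u).

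| u | Calculation | Mean (days) |
|---|---|---|
| 0 | 23 / 2 | 11.5 |
| 0.25 | 33.75 / 2.25 | 15.0 |
| 0.5 | 44.5 / 2.5 | 17.8 |
| 1 | 66 / 3 | 22.0 |

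From the latest injection the mean is 1 day throughout.

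**5. Follow-up to visit 5 after each injection**

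- first: 63 days (58 to 68)
- second: 63 − 21 = 42 days (58 − 24 = 34 to 68 − 18 = 50)
- touch-up: 63 − 42 = 21 days (58 − 45 = 13 to 68 − 39 = 29)

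The chin is followed nominally for 63 days in the down-up group and 42 in the top-down group; for NLF/ML it is the reverse. Between the first injection and visit 3, both groups have the same scheduled follow-up, 21 days (18 to 24), and each has had one area treated only.

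**6. Data available.** Section 8.1.3 records "Affected area" and the start and stop dates of each AE. Section 6.5.5 records the date of administration and "Area of injection".

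**The case against.** Several stronger readings are tempting, and the documents do not support them.

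- A reader might infer that the planned onset summary is distorted. Section 10.4 does not say that onset is counted from the first injection. The figures in steps 3 and 4 show what that rule would do, not what the plan will do. The certain defect is an undefined reference date.
- A reader might infer that chin and NLF/ML events cannot be separated. The recorded areas and dates allow it; the separation is simply not planned.
- A reader might take the singular injection in section 3.1.2 as the onset clock, or as implying only one injection. It sets a collection window.

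There are further fair points for the plan. Section 10.2 likewise refers to the investigational product where a group split would be expected, so the phrase in 10.4 may be template wording and a split by group may be intended. That is plausible, but 10.4 does not say it.

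The contrast between areas is a stated aim for aesthetic improvement and satisfaction, not for safety. Nominal follow-up is 63 days in both groups, so the unequal time per area does not bias a comparison of the two orders. Common injection reactions settle within about a week (section 6.5.3 and Appendix 3), well inside the shortest 34-day window for the second-treated area; unequal follow-up matters mainly for delayed events. These points stand, which is why the comparison by area is offered as descriptive.

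Finally, the synopsis entry on statistical methods is redacted and section 10.7 mentions a statistical plan. A definition may exist there; the point concerns section 10.4 as written.

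**Conclusion.** The point holds as a gap in section 10.4. Read literally, its AE tables form one pooled column and cannot support the safety evaluation of two approaches that sections 2.3 and 10.8 describe. Days to onset has no defined starting point, and the choice shifts individual values by 0, 21 (18 to 24) or 42 (39 to 45) days. Those shifts depend only on Table 1. The means of 11.5 to 22.0 days also rest on an assumed 1-day lag, equal event numbers per injection and an assumed touch-up uptake.

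In a small descriptive study the onset definition alone would be a clarification. Together with the missing split by group and injection period, it decides what the trial can report on safety. The change should be made, ideally before any data are examined, since section 10.6 allows analysis before completion. Nothing here invalidates the design or the data collection.

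**What to change.** Amend section 10.4 in three respects.

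1. Present all AE tables by randomised group and in total.
2. Within each group, tabulate related AEs by injection period (after the first, second and touch-up injections) and by recorded affected area, with the subjects injected at that session as denominator. Show AEs starting before the visit 3 injection as a descriptive randomised comparison of chin only with NLF/ML only.
3. Define days to onset as AE start date minus the date of the most recent preceding injection. For local AEs, use the most recent preceding injection of the affected area. State in the table which rule applied, because one preferred term may contain both kinds.

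The cost is a few sentences and a few descriptive tables from fields already collected, with no new procedures. The drawbacks are small counts per cell and some ambiguity for events in adjoining areas, since the chin treatment includes its surroundings; such events can be flagged in the listing.
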